## **6.5. Compliance with Study Treatment Administration**

At each visit, an evaluation of subject compliance with taken medication will be performed. The investigator will make every effort to bring non-compliant subjects into compliance.

Compliance with GSK2820151 will be assessed through querying the subject during the site visits and documented in the source documents and case report form (CRF).

A record of the number of GSK2820151 tablets dispensed to and taken by each subject must be maintained and reconciled with study treatment and compliance records. Treatment start and stop dates, including dates for treatment delays and/or dose reductions will also be recorded in the CRF.

## **6.6. Treatment of Study Treatment Overdose**

For this study, any dose of GSK2820151 greater than the protocol-specified dose within a 24 hour time period will be considered an overdose.

GSK does not recommend specific treatment for an overdose.

In the event of an overdose the investigator (or treating physician) should:

- Contact the Medical Monitor immediately
- Closely monitor the subject for AEs/SAEs and laboratory abnormalities until GSK2820151 can no longer be detected systemically (at least 28 days for GSK2820151)
- Obtain a plasma sample for PK analysis within 3 days from the date of the last dose of study treatment if requested by the Medical Monitor (determined on a case-by-case basis)

- Document the quantity of the excess dose as well as the duration of the overdosing in the CRF.

Decisions regarding dose interruptions or modifications will be made by the investigator in consultation with the Medical Monitor based on the clinical evaluation of the subject.

## **6.7. Treatment after the End of the Study**

Post study treatment will not be provided as part of the protocol. Upon discontinuation from assigned study treatment, subjects may receive additional (non protocol) therapy at the discretion of the treating physician. New therapy should be documented on the CRF. Every effort should be made to complete the required withdrawal and follow up evaluations prior to initiating further therapy or dosing of an investigational agent (see Section 8.1 for follow-up assessments and procedures).

The investigator is responsible for ensuring that consideration has been given to the post-study care of the subject's medical condition, whether or not GSK is providing specific post-study treatment.

## **7. MEDICATION, DIETARY AND LIFESTYLE RESTRICTIONS**

### **7.1. Concomitant Medications and Non-Drug Therapies**

Subjects will be instructed to inform the investigator prior to starting any new medications from the Screening Visit until the end of the study (Final Study Visit). Any concomitant medication(s), including herbal preparations, taken during the study will be recorded in the eCRF. The minimum requirement is that drug name, route of administration, dose and frequency of dosing, along with start and stop dates of administration should be recorded. Additionally, a complete list of all prior cancer therapies will be recorded in the eCRF.

Questions regarding concomitant medications should be directed to the GSK Medical Monitor for clarification.

If future changes are made to the list of permitted/prohibited medications, formal documentation will be provided by GSK and stored in the study file. Any such changes will be communicated to the investigative sites in the form of a letter.

#### **7.1.1. Permitted Medications and Non-Drug Therapies**

Subjects should receive full supportive care during the study, including transfusions of blood and blood products, and treatment with erythropoietin, antibiotics, antiemetics, antidiarrheals, and analgesics, and other care as deemed appropriate, and in accordance with their institutional guidelines. Colony-stimulating factors like filgrastim and pegfilgrastim may be used as clinically indicated. The only caveat is that subjects should not receive those medications listed as prohibited in Section 7.1.2.1.

Bisphosphonates will be allowed if subjects have been on a stable dose for at least three months prior to receiving the first dose of GSK2820151.

## 7.1.2. Prohibited Medications and Non-Drug Therapies

### 7.1.2.1. Prohibited Medications

The use of certain medications and illicit drugs within 5 half-lives or 28 days (if the drug is a potential enzyme inducer) prior to the first dose of study medication (and for the duration of the study) will not be allowed. If a prohibited medication is required for single use (such as for a procedure) while study treatment(s) is held, the GSK Medical Monitor can approve such use.

Subjects should not receive other anti-cancer therapy [including chemotherapy, radiation therapy, immunotherapy, biologic therapy, investigational therapy, hormonal therapy (other than leuprolide or other LHRH agonists/antagonists), surgery or tumor embolization] while on treatment in this study. Other anti-cancer therapy should not be administered unless one of the following occurs: documented disease progression; unacceptable or unmanageable toxicity; subject is withdrawn from the study at the investigator's discretion or consent is withdrawn; or no further clinical benefit is anticipated which requires permanent discontinuation of study drug. Note, palliative radiation and/or surgical intervention may be permitted (for example to address pain management) and should be discussed with the GSK medical monitor prior to invention to determine appropriate dosing and schedule.

Anticoagulants at therapeutic doses (e.g., warfarin, direct thrombin inhibitors, etc.) are PROHIBITED from seven days prior to the first dose of study drug through completion of the Final Study Visit. Low dose (prophylactic) anticoagulants are permitted provided that the subject's PT/PTT values meet entry criteria.

Subjects may continue to use aspirin, but doses are not allowed to be greater than 100mg per day. The use of non-steroidal anti-inflammatory drugs (NSAIDs) will be excluded, except for when NSAIDs will provide benefit over other analgesics and then to be used with caution, including concomitant use of proton pump inhibitors.

Co-administration of the medications listed in [Table 5](#) are **PROHIBITED** for 5 half-lives (or at least 14 days, whichever is longer) prior to the first dose of study drug until discontinuation from the study drug due to unacceptable risk of Torsades de Pointes (with the exception of **amiodarone** which is prohibited beginning **6 months** prior to Screening through discontinuation from the study. [However, there may be situations when the subject is on study and Advanced Cardiac Life Support (ACLS) requires the use of amiodarone, which should be used as per local clinical guidelines]).

**Table 5 Drugs with a Risk of Torsades de Pointes that are Prohibited**

Amiodarone	Dronedarone	Moxifloxacin
Anagrelide	Droperidol	Papaverine
Azithromycin	Erythromycin	Pentamidine
Chloroquine	Escitalopram	Pimozide
Chlorpromazine	Flecainide	Procainamide
Cilostazol	Fluconazol	Propofol
Ciprofloxacin	Halofantrine	Quinidine
Citalopram	Haloperidol	Roxithromycin
Clarithromycin	Ibogaine	Sevoflurane
Cocaine	Ibutilide	Sotalol
Disopyramide	Levofloxacin	Sulpiride
Dofetilide	Levomepromazine	Sultopride
Domperidone	Levosulpiride	Terlipressin
Donepezil	Methadone	Thioridazine

Data Source: crediblemeds.org revision date 09 January 2017.

Drugs not available/used in the US have been omitted.

The above table is not exhaustive and prohibited drugs are defined by the online version at the time of screening of the subject

If a subject requires medication for hyperemesis, due to the potential of serotonin 5-HT3 receptor antagonists to increase QTcF, palonosetron (up to a maximum dose of 0.25 mg daily) and ondansetron (up to a maximum dose of 8 mg three times daily [TID]) are the only allowed drugs in this class (i.e. dolasetron and granisetron are not permitted).

#### 7.1.2.2. Prohibited Non-Drug Therapies

Non-drug anti-cancer therapies (e.g., radiation therapy, surgery, and/or tumor embolization) will not be permitted from the screening visit through the post-study follow-up visit.

**NOTE:** Subjects may receive focal palliative radiation treatment during this study. Any proposed radiation therapy must be approved by the investigator and the GSK Medical Monitor prior to initiation.

Subjects will abstain from using herbal preparations/medications throughout the study until the final study visit.

Herbal products include, but are not limited to: St. John's Wort, kava, ephedra (ma huang), ginkgo biloba, dehydroepiandrosterone (DHEA), yohimbe, saw palmetto, ginseng.

The investigator should contact a GSK Medical Monitor before initiating treatment with any herbal preparation including marijuana.

### 7.1.3. Cautionary Medications

Co-administration of GSK2820151 and the following medications **requires EXTREME CAUTION** beginning 14 days prior to the first dose of study drug until discontinuation from the study, due to an increased risk of Torsades de Pointes. These medications include (but are not limited to):

**Table 6 Drugs with a Risk of Torsades de Pointes which are permitted for co-administration with Extreme Caution**

Alfuzosin	Foscarnet	Perphenazine
Apomorphine	Gemifloxacin	Pipamperone
Aripiprazole	Hydrocodone ER	Promethazine
Artemimole+piperazine	Iloperidone	Rilpivirine
Asenapine	Imipramine	Risperidone
Atomoxetine	Isradipine	Saquinavir
Bedaquiline	Leuprolide	Sertindole
Buprenorphine	Lithium	Solifenacin
Clomipramine	Melperone	Tacrolimus
Clozapine	Mifepristone	Telavancin
Cyamemazine	Mirabegron	Telithromycin
Degarelix	Mirtazapine	Tetrabenazine
Delamanid	Moexipril/ hydrochlorothiazide	Tiapride
Desipramine	Nicardipine	Tizanidine
Dexmedetomidine	Norfloxacin	Tolterodine
Efavirenz	Nortriptyline	Trimipramine
Ezogabine	Ofloxacin	Tropisetron
Famotidine	Oxytocin	Vardenafil
Felbamate	Paliperidone	Venlafaxine
Fingolimod	Pasireotide	Zotepine
Flupentixol	Perflutren lipid microspheres	Perphenazine

Data Source: crediblemeds.org revision date 09 January 2017.

The above table is not exhaustive and prohibited drugs are defined by the online version at the time of screening of the subject

Drugs not available/used in the US have been omitted

After starting cautionary medications such as in [Table 6](#), it is recommended that ECGs are implemented daily until the steady state of the new medication is reached. If there are ECG abnormalities, implement additional cardiotoxicity monitoring as addressed [Appendix 7](#).

There is a low potential for GSK2820151 to induce or inhibit cytochrome P450 (CYP) enzymes. GSK2820151 has been demonstrated to inhibit Breast Cancer Resistance Protein (BCRP [IC50=3.6 μM]) and thus may alter the metabolism of medications that are substrates of BCRP. These medications include 3-hydroxy-3-methyl-glutaryl-coenzyme

A reductase (HMG-CoA) reductase inhibitors (statins) as well as ciprofloxacin and other fluoroquinolones (though not levofloxacin).

Furthermore, GSK2820151 inhibits P-glycoprotein (PgP) at concentrations  $\geq 100 \mu\text{M}$ . PgP substrates include medications such as statins and digoxin, which may have a narrow therapeutic index. While co-administration of these agents with GSK2820151 is not prohibited, they should be used with caution and additional monitoring for adverse effects should be utilized.

GSK2820151 may also interact with organic anion transporter 3 (OAT3). Substrates of OAT3 include agents such as Penicillin G and indomethacin. While co-administration of these agents with GSK2820151 is not prohibited, they should be used with caution and additional monitoring for adverse effects should be utilized.

Questions regarding concomitant medications should be directed to the GSK Medical Monitor for clarification.

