### 14.7.1. Dose Adjustments for Toxicity

**Table 12 Dose Adjustment/Stopping Safety Criteria**

Toxicity	Dose Adjustment/Stopping Criteria	Management Guidelines
QTcF	If >30msec and < 60 msec change from baseline AND manual QTcF <500 (average of three ECGs over at least 15 minutes)	
 
Continue current dose of GSK2820151               
 
Supplement electrolytes, particularly potassium and magnesium, to recommended levels:                   
 
Maintain serum potassium > 4mol/L
 
Maintain serum magnesium levels >0.85 mmol/L
 
 
 
Discontinue any concomitant medications with potential for QTcF prolongation.
 
Consider 24 hour or longer telemetry monitoring if clinically indicated.
 
 
 

	If $\geq 60$ msec change from baseline occurs  OR  QTcF $\geq 500$  (average of three ECGs over at least 15 minutes)	
 
Discontinue GSK2820151 and notify the GSK Medical Monitor.               
 
Supplement electrolytes to recommended levels:                   
 
Maintain serum potassium > 4mol/L
 
Maintain serum magnesium levels >0.85 mmol/L
 
 
 
Rule out other potential etiologies for prolonged QTcF such as cardiac ischemia
 
Discontinue any concomitant medications with potential for QTcF prolongation.
 
Consider telemetry monitoring if clinically indicated.
 
 
 
This subject may consider restarting study treatment at a previous dose level if the following criteria for QTcF rechallenge are met:               
 
QTcF Rechallenge Procedures: Do not rechallenge with study treatment unless under the following conditions:                   
 
QTcF event reduced to <450 msec,
 
potassium and magnesium levels are within institutional normal range,
 
a favorable risk/benefit profile (in the medical judgement of the Investigator and the GSK Medical Monitor),
 
 
 
 
 

Toxicity	Dose Adjustment/Stopping Criteria	Management Guidelines

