**Section 7.1.3. Cautionary Medications**

**Rationale for change:** The change was made to update the list of drug with a risk of Torsades de Pointes which are permitted for co-administration with extreme caution based on the 2015 guidelines.

**Revised Text:****Table 6 Drugs with a Risk of Torsades de Pointes which are permitted for co-administration with Extreme Caution**

Alfuzosin	lloperidone	Ranolazine
Apomorphine	Isradipine	Rilpivirine
Aripiprazole	Lithium	Risperidone
Atazanavir	Mifepristone	Saquinavir
Atomoxetine	Mirabegron	Tacrolimus
Bedaquiline	Mirtazapine	Telavancin
Clomipramine	Moexipril/HCTZ	Telithromycin
Clozapine	Nicardipine	Tetrabenazine
Desipramine	Norfloxacin	Tizanidine
Dexmedetomidine	Nortriptyline	Tolterodine
Dihydroartemisinin+piperaquine	Ofloxacin	Toremifene
Dolasetron	Olanzapine	Trimipramine
Famotidine	Ondansetron	Vardenafil
Felbamate	Oxytocin	Venlafaxine

Fingolimod	Paliperidone	Ziprasidone
Foscarnet	Pasireotide	
<del>Fosphenytoin</del>	Perflutren lipid microspheres	
Gemifloxacin	Promethazine	
Granisetron	Quetiapine	

Data Source: crediblemeds.org revision date ~~26 September 2014~~ 04 May 2015 Note: This list is not exhaustive. Drugs ~~and/or drug names~~ not available/used in the US have been omitted

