### Section 7.1.3 Cautionary Medications

**Rationale for change:** The change was made to update the list of drug with a risk of Torsades de Pointes which are permitted for co-administration with extreme caution based on the 2017 guidelines mentioned on crediblemeds.org.

**Revised Text:****Table 6 Drugs with a Risk of Torsades de Pointes which are permitted for co-administration with Extreme Caution**

Alfuzosin <del>Alfuzosin</del>	Foscarnet <del>lloperidone</del>	Perphenazine <del>Ranolazine</del>
Apomorphine <del>Apomorphine</del>	Gemifloxacin <del>Isradipine</del>	Pipamperone <del>Rilpivirine</del>
Aripiprazole <del>Aripiprazole</del>	Hydrocodone ER <del>Lithium</del>	Promethazine <del>Risperidone</del>
Artemimole+piperavaquine <del>Atazanavir</del>	lloperidone <del>Mifepristone</del>	Rilpivirine <del>Saquinavir</del>
Asenapine <del>Atomoxetine</del>	Imipramine <del>Mirabegron</del>	Risperidone <del>Tacrolimus</del>
Atomoxetine <del>Bedaquiline</del>	Isradipine <del>Mirtazapine</del>	Saquinavir <del>Telavancin</del>
Bedaquiline <del>Clomipramine</del>	Leuprolide <del>Moexipril/Hydrochlorothiazide (HCTZ)</del>	Sertindole <del>Telithromycin</del>
Buprenorphine <del>Clozapine</del>	Lithium <del>Nicardipine</del>	Solifenacin <del>Tetrabenazine</del>
Clomipramine <del>Desipramine</del>	Melperone <del>Norfloxacin</del>	Tacrolimus <del>Tizanidine</del>
Clozapine <del>Dexmedetomidine</del>	Mifepristone <del>Nortriptyline</del>	Telavancin <del>Tolterodine</del>
Cyamemazine <del>Dihydroartemisinin+piperavaquine</del>	Mirabegron <del>Ofloxacin</del>	Telithromycin <del>Toremifene</del>
Degarelix <del>Delasetron</del>	Mirtazapine <del>Olanzapine</del>	Tetrabenazine <del>Trimipramine</del>
Delamanid <del>Famotidine</del>	Moexipril/ hydrochlorothiazide <del>Ondansetron</del>	Tiapride <del>Vardenafil</del>
Desipramine <del>Felbamate</del>	Nicardipine <del>Oxytocin</del>	Tizanidine <del>Venlafaxine</del>
Dexmedetomidine <del>Fingolimod</del>	Norfloxacin <del>Paliperidone</del>	Tolterodine <del>Ziprasidone</del>
Efavirenz <del>Foscarnet</del>	Nortriptyline <del>Pasireotide</del>	Trimipramine

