**Table 5 Drugs with a Risk of Torsades de Pointes that are Prohibited**

Amiodarone	Dronedarone	Moxifloxacin
Anagrelide	Droperidol	Pentamidine
Azithromycin	Erythromycin	Pimozide
Chloroquine	Escitalopram	Procainamide
Chlorpromazine	Flecainide	Quinidine
Citalopram	Halofantrine	Sevoflurane
Clarithromycin	Haloperidol	Sotalol
Cocaine	Ibutilide	Thioridazine
Disopyramide	Levofloxacin	
Dofetilide	Methadone	

Data Source: crediblemeds.org revision date 26 September 2014

At time of screening, if a subject is currently receiving any of the listed prohibited medications/substances, the medication or substance must be discontinued for a period of 5 half lives (or at least 14 days, whichever is longer) prior to the administration of the first dose of study drug in order for the subject to meet study eligibility.

If a subject requires medication for hyperemesis, due to the potential of serotonin 5-HT3 receptor antagonists to increase QTcF, palonosetron (up to a maximum dose of 0.25 mg daily) and ondansetron (up to a maximum dose of 8 mg three times daily [TID]) are the only allowed drugs in this class.

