**Table 6 Drugs with a Risk of Torsades de Pointes which are permitted for co-administration with Extreme Caution**

Alfuzosin	lloperidone	Quetiapine
Apomorphine	Isradipine	Ranolazine
Aripiprazole	Lithium	Rilpivirine
Atazanavir	Mifepristone	Risperidone
Bedaquiline	Mirabegron	Saquinavir
Clozapine	Mirtazapine	Tacrolimus
Dexmedetomidine	Moexipril/HCTZ	Telavancin
Dihydroartemisinin+piperazine	Nicardipine	Telithromycin
Dolasetron	Norfloxacin	Tetrabenazine
Famotidine	Oxofloxacin	Tizanidine
Felbamate	Olanzapine	Tolterodine
Fingolimod	Oxytocin	Vardenafil
Foscarnet	Paliperidone	Venlafaxine
Fosphenytoin	Pasireotide	Ziprasidone
Gemifloxacin	Perflutren lipid microspheres	
Granisetron	Promethazine	

Data Source: crediblemeds.org revision date 26 September 2014

Note: This list is not exhaustive. Drugs and/or drug names not available/used in the US have been omitted. After starting cautionary medications such as in [Table 6](#), it is recommended that ECGs are implemented daily until the steady state of the new medication is reached. If there are ECG abnormalities, implement additional cardiotoxicity monitoring as addressed [Appendix 7](#).

There is a low potential for GSK2820151 to induce or inhibit cytochrome P450 (CYP) enzymes. GSK2820151 has been demonstrated to inhibit Breast Cancer Resistance Protein (BCRP [IC50=3.6 μM]) and thus may alter the metabolism of medications that are substrates of BCRP. These medications include HMG-CoA reductase inhibitors (statins) as well as ciprofloxacin and other fluoroquinolones (though not levofloxacin).

Furthermore, GSK2820151 inhibits P-glycoprotein (PgP) at concentrations ≥ 100 μM. PgP substrates include medications such as statins and digoxin, which may have a narrow therapeutic index. While co-administration of these agents with GSK2820151 is not prohibited, they should be used with caution and additional monitoring for adverse effects should be utilized.

GSK2820151 may also interact with organic anion transporter 3 (OAT3). Substrates of OAT3 include agents such as Penicillin G, indomethacin, and ciprofloxacin. While co-administration of these agents with GSK2820151 is not prohibited, they should be used with caution and additional monitoring for adverse effects should be utilized.

Questions regarding concomitant medications should be directed to the GSK Medical Monitor for clarification.

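### Table 6 permits tropisetron with extreme caution, although Section 7.1.2.1 allows only palonosetron and ondansetron among the 5-HT3 antagonists

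*Protocol*

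**What the plan says.** Section 7.1.3 permits a list of drugs alongside GSK2820151 under the title "Drugs with a Risk of Torsades de Pointes which are permitted for co-administration with Extreme Caution". Tropisetron is in the third column. For drugs started from this table the section recommends daily ECGs until the new drug reaches steady state, so a listing works as a permission with monitoring attached.

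Section 7.1.2.1, below Table 5, deals with antiemetics separately. Because 5-HT3 antagonists can lengthen QTcF, it names palonosetron (at most 0.25 mg daily) and ondansetron (at most 8 mg three times daily) and says that these "are the only allowed drugs in this class (i.e. dolasetron and granisetron are not permitted".

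Two other places say which section governs. Section 7.1.1 allows antiemetics as supportive care, subject to the prohibitions of Section 7.1.2.1. Exclusion criterion 4 in Section 5.2 excludes current or planned use of forbidden medication and points to Section 7.1.2 for the list.

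**The concern.** A site that looks up tropisetron in Table 6 finds it allowed with caution. A site that reads the class rule in Section 7.1.2.1 finds it barred. The parenthesis in that rule names only dolasetron and granisetron as not permitted, so even someone who checks both places could suppose that tropisetron was left available on purpose.

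The rule exists to limit QT risk. Section 4.6.1 reports QT prolongation in dogs, calls the risk of torsades unclear, and describes gastrointestinal effects as dose limiting in rats and dogs. Table 3 gives nausea and vomiting their own dose-limiting toxicity criteria. A need for antiemetics was therefore foreseeable, and the choice among them is one that sites would have had to make. What is at stake is an extra QT-active antiemetic given to a subject on a drug whose own QT effect was still being studied.

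**Working it through.** No formula or stated figure applies. The check sets the texts side by side and then traces the list through its versions.

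**Step 1: the current text**

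| Place | Rule | Tropisetron |
|---|---|---|
| Section 7.1.2.1, text under Table 5 | Palonosetron and ondansetron only, within the 5-HT3 class | Barred, as a member of the class |
| Section 7.1.3, Table 6 | Listed drugs permitted with extreme caution | Permitted |

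The one input from outside the documents is the drug's class. Given that, both rows cannot hold.

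**Step 2: how the list changed**

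Counting the drugs in Table 6 whose names end in -setron:

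| Version | Drugs in table | Names ending in -setron | Of these, outside the two-drug rule |
|---|---|---|---|
| Original protocol | 46 | dolasetron, granisetron | 2 |
| Amendment 1 log | 52 | dolasetron, granisetron, ondansetron | 2 |
| Current (Amendment 4) | 62 | tropisetron | 1 |

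The current count is 21 rows × 3 columns = 63 entries. Perphenazine appears twice, so there are 63 − 1 = 62 distinct drugs. The Amendment 1 count leaves out fosphenytoin, which that log strikes through.

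The two-drug limit was already in the original protocol ("three times daily [TID]) are the only allowed drugs in this class"), whose Table 6 rested on an earlier release of the external list ("Data Source: crediblemeds.org revision date 26 September 2014"). Amendment 1 refreshed the table ("permitted for co-administration with extreme caution based on the 2015 guidelines") and Amendment 4 did so again ("permitted for co-administration with extreme caution based on the 2017 guidelines mentioned on crediblemeds.org"). The Amendment 4 log strikes dolasetron, granisetron and ondansetron from Table 6 and adds tropisetron. It also shows the Section 7.1.2.1 sentence with its parenthesis barring dolasetron and granisetron by name.

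The change log is used here only to explain the origin of the entry. The contradiction itself lies wholly in the current text.

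**Step 3: which of the two is wrong**

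Section 7.1.1 subjects antiemetics to Section 7.1.2.1, and exclusion criterion 4 points to Section 7.1.2. Both give precedence to the prohibited-medication section. The two-drug rule has stood since the original protocol, and the last update took out of Table 6 the two drugs that then broke it. All of this points to the tropisetron entry as a slip made when the table was refreshed.

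**Step 4: size**

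1 / 62 = 1.6% of the drugs in Table 6. This is a share of a list and measures neither risk nor exposure. The documents give no frequency of use.

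**The case against.** The best defence is that the protocol already settles the matter. Section 7.1.1 makes the prohibitions of Section 7.1.2.1 the limit on antiemetics, exclusion criterion 4 points the same way, and the class rule is explicit. Only a site that read Table 6 alone would go wrong. This is correct about precedence, and it is why the fix is to remove the entry and leave the rule as it is. It does not remove a permission that contradicts the rule. Tropisetron is also not named in Table 5, so it is barred only through the class wording, which is easier to miss.

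The footnote to Table 6 might also be cited, since it defers to the online list at the time of screening for which drugs are prohibited. But the two-drug limit is the protocol's own rule and does not come from that list.

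A reader might infer a second, larger fault in the QTcF rows of Table 12. In the band above 30 and below 60 msec the row says "Continue current dose of GSK2820151" and also "Discontinue any concomitant medications with potential for QTcF prolongation". Amendment 4 added leuprolide and degarelix to Table 6, while exclusion criterion 2c wants prostate cancer subjects to stay on LHRH therapy. The row could then seem to stop that therapy with nobody named to decide. The documents do not support this reading:

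- The introduction to Appendix 7 calls the criteria guidance that does not replace clinical judgment. It has the investigator judge which drug may be contributing, and it calls for dose modifications to be discussed with the GSK Medical Monitor.
- Sections 7.1 and 7.1.3 both direct questions about concomitant medication to the Medical Monitor.
- The instruction to stop such drugs is in the original protocol in the same words, so Amendment 4 did not create it.

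A sentence on LHRH agents would be a drafting preference, not the correction of an error.

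**Conclusion.** The tropisetron entry in Table 6 contradicts Section 7.1.2.1 and is wrong as written. The conclusion rests on one assumption, that tropisetron is a 5-HT3 antagonist.

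Severity is minor. The controlling rule is clear once found, and both allowed drugs of the class remain available. A reader might infer that the slip put subjects at risk or affected the results. Nothing in the documents shows that any subject received tropisetron. Section 1 of the SAP reports 5 subjects enrolled and restricts the output to listings, and no planned analysis turns on this entry.

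**What to change.** Delete tropisetron from Table 6 in Section 7.1.3. Leave the two-drug rule in Section 7.1.2.1 and the QTcF rows of Table 12 as they are. The cost is one removed table entry, with no added procedures, visits or subjects.
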